## **17.0 Financial Compensation:**

Upon completion of study tasks, participants will be paid an hourly rate for participation (\$15/hr). Payment will be made in cash at the conclusion of each study visit. If a subject decides to withdraw from the study before its completion, s/he will still be paid \$15 per hour for the time spent. In the event that a participant is removed from the study without their consent, compensation will be pro-rated based upon the duration the participant remained compliant with study tasks and procedures. Participants who remain enrolled through the entire duration of the study will receive a \$50 completion bonus.

## **18.0 Audio/Video Recording/Photography**

We will give participants the option of declining to be audio recorded during this experiment (for data collection). The objective of this audio recording is to be able to have internal lab staff reliability discussions to ensure test reliability and accuracy.

When recorded, participant anonymity will be maintained (i.e. name is not being said, filename is de-identified). Participants will document on the consent forms whether or not they agree to being recorded, or if recording is not applicable for a specific experiment. Recordings will be kept and used for lab staff only and will be destroyed once data analysis is complete.

## **19.0 Potential Benefits to Participants:**

Although participants in this study may not directly benefit from participation, many people are attracted to hearing aid research as an opportunity to learn about their hearing and ask questions about hearing aids and assistive listening devices (such as a remote microphone) without sales pressure. Participants who had been unaware of remote microphones or unsure if they would benefit may find the study helps them determine if it is something they would like to pursue with their hearing health provider. All participants in the study will have the opportunity to receive counseling at the end of the study, done by the investigator, including listening recommendations tailored to their individual speech understanding, memory and attention. They will have a chance to ask questions and receive information about options for their hearing loss (outside of the study).

## **20.0 Risks to Participants:**

All study procedures pose minimal risk to study participants. Some of the study tasks can be boring, or repetitive. If a participant wishes to discontinue testing at any point they may choose to do so without any consequence. Additionally, listeners who receive poor scores on the attention and memory tests may be disappointed to learn of their performance. There is a possibility that some people may find some of the questionnaires uncomfortable. Participants will be told they do not need to answer any question or questions that make them uncomfortable. Participants will not be removed from the study

for declining to answer part of all of the questionnaires. Some participants may find the hearing aid settings used in this study to be loud or sharp in comparison to their own hearing aid settings. These are all normal and expected consequences of new hearing aids.

If an earmold impression is taken, participants may experience some temporary discomfort or a ticklish feeling as the cotton or foam block is placed into the ear canal. Participants may also notice that the impression material is slightly cold, or experience a feeling of pressure while the impression material is in your ear. Rarely, there can be some minor abrasions to the skin of the ear canal. These procedures are routinely used when fitting hearing aids or creating custom earplugs and the risks in this study are no higher than the risks that would be experienced in an audiology clinic.

If the investigator determines participation in the study places a subject at an unacceptable level of risk, enrollment or study tasks will not proceed.

If a research participant decides to withdraw or discontinue study procedures all data collected up to that point can be used by the investigator unless the participant indicates they would like to have their data removed from the study. Once a participant is unable to continue with the study, compensation will end.

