## 2.0 Objectives:

Despite improvements in digital hearing aid technology, many individuals with hearing loss continue to report difficulty understanding speech in challenging listening environments. Remote microphones have been shown to provide benefit in many of the most common challenging listening environments: distant speakers, background noise and reverberation. Despite demonstrated benefit, there is a low rate of remote microphone use amongst adults with hearing impairment. One reason for low uptake may be an uncertainty amongst hearing healthcare providers and potential users regarding expected clinically relevant benefit. This clinical trial, funded by Sonova, will attempt the following:

1. To describe the range of Roger remote microphone benefit among adults with mild-to-moderate sensorineural hearing loss
2. To determine specific individual factors beyond the audiogram that are associated with greater Roger remote microphone benefit.

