## 4.0 Study Endpoints

Primary Endpoint: Benefit from use of a remote microphone.

1. Abbreviated Profile of Hearing Aid Benefit (APHAB): This is a measure of hearing aid benefit that is standard in clinical practice. Participants will complete this questionnaire to compare perceived aided benefit with hearing aid alone vs hearing aid+ remote microphone.

Secondary Endpoints: In order to build a better profile of patients who may benefit from a remote microphone, several measures of hearing ability, manual dexterity, personality, and social activity are included.

2. Audiometric evaluation including hearing and health history, air and bone condition testing, measurement of loudness discomfort level and real-ear assessment of current hearing aids. These are all standard clinical assessments.
3. MoCA test: The Montreal Cognitive assessment is a cognitive screening test designed to detect mild cognitive impairment. It requires approximately 10 minutes and assesses short-term recall, visuospatial abilities, executive function, attention, working memory, language, and orientation to time and place.
4. Practical Hearing Aid Skills Test-Revised (PHAST-R)- will be used to ensure participants are able to use the trial devices
5. Unaided and Aided speech in noise testing: This is a standard clinical measure of an individual's ability to hearing and understand speech in background noise.
6. Speech, Spatial, and Quality of Hearing Scale (SSQ) pre- and post- Roger use: Evaluates an individual's perceptions of their hearing abilities in a variety of every day scenarios.
7. Acceptable Noise Level (ANL): This test has been shown to be correlated with successful hearing aid use.
8. LiSN-S: Spatial auditory information assessment. This test has been shown to correlate with successful assistive listening device use.
9. Level of social activity, using the HRS Activities and Time Use subscale
10. Personality, using the Positive and Negative Affectivity Scale (PANAS) and International Personality Item Pool (IPIP). Personality has been shown to be related to successful hearing aid use.
11. Self-efficacy, using the Generalized Self-Efficacy Scale. Self-efficacy is an individual's belief in his/her ability to achieve a goal and has been linked with hearing device satisfaction.

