## 6.0 Procedures Involved:

Approach: The trial will use a within-subjects design consisting: 1)Baseline assessments (see assessments), 2) Being fit with trial hearing aids for a two week adjustment period, 3) Roger connect fitting appointment, 3) Approximately four-week trial period of Roger use in the participant's everyday environment(s), 4) Final visit with outcome measures.

Participants whose hearing loss qualifies them for a dome mold fitting (non-custom) will start their trial the same day as their eligibility assessment. Participants whose hearing loss or ear structure requires a custom mold fitting will have earmold impressions taken at their eligibility assessment and then be fit with the trial devices after the custom earmold has arrived back in the lab, usually about one to two weeks later. During an earmold impression the ear is visually inspected with an otoscope (magnifying scope with light). A cotton or foam block and soft impression material are placed in the ear and sets for approximately 3 minutes. The resulting impression is used to order an earmold for later testing. This is a standard clinical procedure.

A licensed clinical audiologist will perform the assessments, fitting and counseling of hearing aids and Roger system, and conduct the outcome measures. To ensure appropriate fit and use by the participants, there will be a follow-up one week after receiving the Roger. During this appointment participants will be evaluated, and their hearing aid logging will be checked for compliance.

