Hearing aid/Roger fitting: Trial hearing aids and clinically-appropriate earmolds or domes will be provided by Sonova at no charge to the participants for the duration of the trial. The Marvel 90 hearing aids are Phonak's advanced technology level and to provide datalogging via 7 base programs. Aids will be set to NAL-NL2 targets using probe microphone measurements. Directional microphones will be enabled and verified via probe-microphone testing. Roger will be verified via probe-microphone testing, following clinical best practice. Appropriate hearing aid adjustments (as judged by the study audiologist) will be permitted to provide acceptable sound quality and loudness. Final REARs will be recorded. Participants will be fit with the trial hearing aids and wear them for two weeks prior to receiving the Roger device. This is to allow participants to adjust to the sound quality of a new pair of hearing aids and ensure that measured differences are due to Roger use and not the newer hearing aids. The study audiologist will instruct participants regarding hearing aid and Roger device use. PHAST-R and a Roger competency questionnaire (to be developed with input from Phonak) will be used to document understanding of device function at the fitting and one-week follow-up appointments. Participants will then wear the hearing aids and use the Roger system for 1

month in their everyday listening environments. At the completion of the trial, participants will return to the lab for outcome assessments and to provide spontaneous feedback regarding their experiences. Hearing aids will be returned to the study site following completion of the trial.

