## **10.0 Sample Size:**

Northwestern plans to enroll 40 total participants.

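### Participants who leave after Roger fitting but before the final visit have no with-Roger APHAB or SSQ; if leaving is related to poor benefit, the reported range may be cut off at its low end

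*Protocol*

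**What the plan says.** Section 2.0 gives as the first objective "To describe the range of Roger remote microphone benefit among adults with mild-to-moderate sensorineural hearing loss"; the second is to find individual factors associated with greater benefit. Section 4.0 makes benefit the primary endpoint, measured by the APHAB, which is to "compare perceived aided benefit with hearing aid alone vs hearing aid+ remote microphone". The SSQ before and after Roger use is a secondary endpoint.

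Section 6.0 fixes the timing. The design ends with "4) Final visit with outcome measures", and the fitting paragraph repeats it: "At the completion of the trial, participants will return to the lab for outcome assessments". The one scheduled visit between Roger fitting and the final visit is the one-week follow-up. There participants are evaluated, "their hearing aid logging will be checked for compliance", and the PHAST-R and a Roger competency questionnaire are given. Neither the APHAB nor the SSQ is named at that visit.

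On leaving early, section 20.0 says: "If a research participant decides to withdraw or discontinue study procedures all data collected up to that point can be used by the investigator". People who leave may also ask to have their data taken out. Section 17.0 foresees removal without the participant's consent, but only to settle payment: "compensation will be pro-rated based upon the duration the participant remained compliant with study tasks and procedures". No section describes an outcome assessment at exit.

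Section 10.0 gives the sample size: "Northwestern plans to enroll 40 total participants". It states no dropout allowance.

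**The concern.** The with-Roger half of the primary comparison is scheduled at one time point, the last. A participant who is fitted with Roger and leaves in week one, two or three contributes a baseline and no benefit score.

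This bears directly on both objectives. A description of range depends on its tails, and people who find a device unhelpful or hard to handle may be more likely to leave. If so, the reported range would start too high and the mean would be too favourable. The candidate predictors in section 4.0 include dexterity, self-efficacy and working memory. If these also influence who leaves, the associations sought under Objective 2 would be estimated in a selected group.

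Handling of missing scores can be left to an SAP. Whether a score is ever collected cannot: it depends on the visit schedule and the exit procedure, which the protocol fixes.

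**Working it through.** **Step 1. Who lacks a score under the schedule as written?**

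| Situation | With-Roger APHAB/SSQ provided for? |
|---|---|
| Completes about four weeks and attends the final visit | Yes (section 6.0) |
| Stops using Roger but stays in the study | Yes, if they attend the final visit; section 6.0 sets no minimum use, but does not explicitly ask non-users to attend |
| Withdraws, discontinues study procedures or is removed after Roger fitting | No (sections 6.0, 17.0, 20.0) |
| Leaves during the two weeks with hearing aids only | No, but there is no Roger benefit to measure |

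The gap is the third row.

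**Step 2. Inputs for size.** N = 40 (section 10.0). The protocol gives no derivation of this number, so there is no figure to reproduce. Dropout is not stated; I assume 5-20%, that is 2 to 8 of 40. Benefit is expressed in SD units and taken as normal, also an assumption.

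**Step 3. Worst case in closed form: the lowest fraction p is lost.** Let a be the p-quantile of the standard normal and φ its density.

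- Mean of those left: L = φ(a)/(1 − p). For p = 0.10, φ(1.2816)/0.9 = 0.195. For p = 0.20, φ(0.8416)/0.8 = 0.350.
- SD of those left: √(1 + aL − L²), with a = −1.2816 or −0.8416, gives 0.844 or 0.764.
- The 10th percentile of those left is the original quantile at p + 0.1(1 − p). For p = 0.10 that is the 19th percentile, −0.88 SD. For p = 0.20 it is the 28th, −0.58 SD. The untruncated value is −1.28 SD.

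**Step 4. Simulation with 40 participants** (40,000 replicates; d scores lost). With all 40 scores, the expected minimum is −2.16, the mean 0 and the SD 0.99. In the moderate case the d participants lost are those lowest on a variable correlated 0.5 with benefit.

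| Lost (left) | Lowest lost: minimum / mean / SD | Moderate selection: minimum / mean | Random loss: minimum / mean |
|---|---|---|---|
| 2 (38) | −1.51 / +0.10 / 0.90 | −2.02 / +0.05 | −2.14 / 0 |
| 4 (36) | −1.20 / +0.19 / 0.84 | −1.93 / +0.09 | −2.12 / 0 |
| 6 (34) | −0.98 / +0.27 / 0.80 | −1.84 / +0.13 | −2.09 / 0 |
| 8 (32) | −0.79 / +0.34 / 0.76 | −1.77 / +0.17 | −2.07 / 0 |

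The worst-case columns agree with step 3. Moderate selection gives about half the worst-case shift in the mean. Random loss leaves the mean alone and barely moves the minimum.

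**Step 5. Would more enrolment help?** Keeping 40 evaluable needs 40/(1 − dropout), rounded up: 43, 45, 48 or 50 at 5, 10, 15 or 20%. This restores the number of scores but does not remove a selective loss.

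**The case against.** The strongest reply is that much of what one might read into these sections is not there.

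- A reader might infer that anyone who stops using Roger loses their score. The documents do not say so. Section 20.0 speaks of withdrawing or discontinuing study procedures, and section 6.0 attaches no use condition to the final visit. The $50 bonus in section 17.0 rewards staying enrolled throughout, not wearing the device. This part of the reply stands.
- A reader might join the log check in section 6.0 to the compliance wording in section 17.0 and infer that low users are removed. No such rule is stated. The log check is presented as a way to secure proper fit and use, and section 17.0 only sets how pay is pro-rated after a removal. This also stands.
- The quoted sentence in section 20.0 permits use of data already collected; it does not forbid collecting more at exit. True, but no other section provides for it, so the gap remains.
- Dropout may be low: about six weeks, minimal risk, hourly pay, experienced hearing aid users. This is reasonable and limits the likely size, but the protocol gives no figure either way.
- Exit scores after one to three weeks of Roger are not the same measurement as scores after four. This is fair, and it is why they should be flagged and the range shown both ways.

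**Conclusion.** The point holds as a gap in data collection. Participants who leave or are removed after Roger fitting and before the final visit have no with-Roger APHAB or SSQ, and nothing done at analysis can supply them.

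The consequence is conditional. It would be tempting to say that the reported range does lose its low end, but that needs both material dropout and a link between leaving and poor benefit, and the documents give neither. With an assumed 10-20% loss and normally distributed benefit, the mean is overstated by about 0.20-0.35 SD in the worst case, 0.09-0.17 SD under moderate selection and zero under random loss. The expected minimum moves from −2.16 SD to between −1.20 and −0.79 in the worst case, to between −1.93 and −1.77 under moderate selection, and only to between −2.12 and −2.07 under random loss.

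This is a cheap improvement that protects both objectives, not an error that invalidates the design.

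**What to change.** Amend sections 6.0 and 20.0 as follows.

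1. State that participants who stop using Roger are still asked to attend the final visit and complete the APHAB and SSQ.
2. Offer both questionnaires at exit to anyone who leaves or is removed after Roger fitting, at device return or by phone or mail. Record the date and the main reason for leaving.
3. Report the range of benefit with and without these early scores, flagged for shorter Roger exposure. Report how many participants have no score, and why.

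The right to leave at any time, to decline questions and to ask for data removal stays as it is.

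Cost: a short amendment and two questionnaires already in use. Section 5.0 already logs device returns, but section 6.0 describes return only after completion, so the phone or mail route is needed for early leavers. The downside is that exit scores reflect less than four weeks of use, which the two-way reporting makes visible.

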## **21.0 Provisions to Protect the Privacy and Confidentiality of Participants and the Research Data:**

During the consent process a lab member will explain that their identifiable information will not be used. Each participant will receive a study code that will be used for all study data. The only link between identifiable data and a study code will be on a password protected HIPAA-approved server with server security managed by Northwestern School of Communication computer staff. Any physical data containing identifiable participant information (i.e. consent documents) are kept under lock and key accessible only by study staff.

## **22.0 Data Monitoring Plan to Ensure the Safety of Participants:**

N/A

## **23.0 Data, and if applicable, Specimen Banking:**

N/A

## **24.0 Data Sharing:**

This project is funded by Sonova and data may be shared with their research staff for the purposes of developing better fitting protocols for remote microphones. Any data shared will be de-identified. Physical files in our lab are kept in a locked filing cabinet. Any data stored electronically is de-identified.

